10.4 Safety Monitoring and Stopping Rule

The Phase II study is a randomized, double blind, placebo-controlled study. To ensure the safety of the patients enrolled in the Phase II study, Bayesian stopping boundaries are used to allow early stopping at any given time in the combined population. The objective response rate (ORR) and toxicity of CD24Fc during the whole study will be monitored simultaneously using the Bayesian stopping boundaries calculated based on beta-binomial distribution. Toxicity is defined as new AE of \geq grade 3 that are

outside the spectrum of irAEs. ORR is defined as partial response and complete response by RECIST V1.1 after retreatment with ICI.

The regimen will be considered safe if the ORR is at least 20% in all patients in both arms and the toxicity rate is maintained at most 33.3% for the CD24Fc arm. Previous studies for controls suggested the ORR after retreatment with ICI is about 20-40%, and therefore we consider a response rate <20% in all patients in both arms as unacceptable, which will indicate an effect of CD24Fc on promoting tumor growth. The prior probabilities of response and toxicity for the regimen are modeled by beta distributions [Beta(0.8, 1.2) and Beta(0.3, 1.7), respectively], and response and toxicity are assumed to be independent. Denoting the probabilities of response for both arms and toxicity for CD24Fc arm by $\{\theta_{RES}, \theta_{TOX}\}$, and they are compared to fixed targets of response and toxicity rates. The following decision criteria will be applied:

- 1) stop if $\text{Prob}\{\theta_{RES} < 0.2 \mid \text{data}\} > 0.97$, and
- 2) stop if $\text{Prob}\{\theta_{TOX} > 0.333 \mid \text{data}\} > 0.97$

We will have randomization box of 6 patients and thus ensure that 3 patients have been dosed for each 6 subjects enrolled. Patients will be monitored by a cohort size of 6 patients (3 for the CD24Fc arm and 3 for the placebo arm) according to the following stopping boundary for toxicity during the whole study. To be conservative, we attribute all AEs to CD24Fc.

Number of Patients Evaluated in All Enrolled Patients (half control and half CD24Fc)	Stop if Number of ORR Observed	Stop if Number of AE Observed
6	Never stop with these many patients	Never stop with these many patients
12	Never stop with these many patients	≥ 5
18	0	≥ 7
24	≤ 1	≥ 8
30	≤ 2	≥ 10
36	≤ 2	≥ 11
42	≤ 3	≥ 12
48	≤ 4	≥ 14
54	≤ 5	≥ 15
60	≤ 6	≥ 16
66	≤ 7	≥ 17
72	Always stop with this number of patients	

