6.1.1 Phase II Randomized Double Blind Placebo Controlled Study

Phase II study will consist of a randomized double blind placebo controlled study involving patients who have treatment interruption due to grade 2 or 3 irAEs. Patients may receive steroids at the discretion of the treating physician prior to and during treatment with CD24Fc. As the steroids is the most commonly used SOC therapy for irAEs and it affects the severity and duration of irAE, we will separate the subjects into two groups based on the status of steroids use at registration. Each group of patients will be randomized (1:1) to receive CD24Fc vs placebo in addition to SOC treatment for irAE. Patients who are randomized to treatment with CD24Fc will receive treatment every 2 weeks for total of three treatments. Placebo group will receive 100 mL of normal saline every 2 weeks for total of three treatments. Refer to [Table 2](#) and [Figure 2](#) for treatment schedule. All patients shall complete 3 treatments.

Two weeks after completing the third treatment dose, patients will be re-evaluated for retreatment with ICI at the discretion of the treating physician and post treatment re-evaluation. Thereafter, patients will continue to end of treatment safety follow up on day 60. After the end of treatment, we will follow patients with irAE and survival by chart check every 3 months for up to 1 year.

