10.2 Statistical Analysis

Demographic and background characteristics obtained at enrollment will be listed and summarized. Descriptive statistics will be used to summarize changes of biomarkers from baseline in clinical laboratory parameters for this cohort, and use of steroids (drug, dose, duration) and other treatment for irAE. We will adjust steroids use in analyses. Subgroup analyses will be performed separately by the status of Steroids use.

To assess toxicity: Toxicity is evaluated by NCI CTCAEv5.0. The type, grade, frequency and proportion of toxicities noted during the treatment period will be reported, along with associated 95% confidence interval of proportion. All adverse events noted by the investigator will be tabulated according to the affected body system. In phase I lead-in study, dose limiting toxicity is defined as any new AE of \geq grade 3 that are outside the spectrum of irAEs.

To assess time to recovery from irAE (time to reduction of irAE by at least one grade), time to all irAEs reduced to ≤ 1 , and time to resume ICI treatment: All time points will be started from Day 1 of CD24Fc treatment. Kaplan-Meier plots and confidence intervals will be used to summarize outcomes. Medians and associated 95% confidence intervals will be calculated, and comparisons between groups will be

performed by log-rank tests. Cox proportional hazard models will be used to explore association between covariates and outcomes.

To assess recovery rate of CD24Fc (reduction of irAE by at least one grade) at D42 and response rate of ICI: The fraction of patients who experience a PR or CR will be determined by dividing the number of responders by the total evaluable patients. The fraction will be reported along with 95% two-sided confidence intervals. Comparisons between groups will be performed by Fisher's Exact tests. We will also characterize the proportion who remain that either respond or have stable disease, compared to those who progress.

To assess PFS and OS: Kaplan-Meier plots and confidence intervals will be used to summarize PFS, and OS; 1-year OS rate will be reported; medians and associated 95% confidence intervals will be calculated, and comparisons between groups will be performed by log-rank tests. Cox PH models will be used to explore association between outcomes and covariates.

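### Section 10.4 reads a pooled response rate below 20% as a CD24Fc effect, but that rests on an external benchmark: the pooled rate does not show which arm lost response, and its denominator is inconsistent

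*Combined protocol and SAP*

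**What the plan says.** Section 10.4 sets a Bayesian rule on response and another on toxicity, with looks every six patients, three per arm. The parameters are introduced as follows: "Denoting the probabilities of response for both arms and toxicity for CD24Fc arm by" θ_RES and θ_TOX. So response is pooled over the arms. Controls in previous studies are said to have had an ORR of about 20-40% after ICI retreatment, and from this the section takes "a response rate <20% in all patients in both arms as unacceptable, which will indicate an effect of CD24Fc on promoting tumor growth".

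Four places bear on who is counted for ORR:

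- Section 10.4: "ORR is defined as partial response and complete response by RECIST V1.1 after retreatment with ICI".
- Section 6.1.1, on what happens after the third dose: "patients will be re-evaluated for retreatment with ICI at the discretion of the treating physician".
- The stopping table in 10.4 is indexed by "Number of Patients Evaluated in All Enrolled Patients (half control and half CD24Fc").
- Section 8.0.2.0 treats every patient as evaluable for response. Section 10.2, under "To assess recovery rate of CD24Fc (reduction of irAE by at least one grade) at D42 and response rate of ICI", divides responders by the total evaluable. It plans a Fisher comparison between groups but gives it no interim timing.

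For toxicity the aim is that "the toxicity rate is maintained at most 33.3% for the CD24Fc arm", and the section adds "To be conservative, we attribute all AEs to CD24Fc".

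**The concern.** A pooled rate can fall because both arms respond poorly or because only the CD24Fc arm does. It can also stay above the boundary when responses disappear on CD24Fc, because placebo responses hold it up. The trial has a randomised placebo arm that could separate these cases, but the interim rule does not use it.

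This is the only interim rule on tumour response. Section 13.0 gives the DSMC accrual logs and adverse-event information monthly, and no section gives it ORR by arm. At stake are two errors: a stop attributed to CD24Fc when the population simply responds less than the benchmark, and a real loss of response on CD24Fc that goes unnoticed.

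**Working it through.** **Inputs, all from 10.4.** Response prior Beta(0.8, 1.2); limit 0.20; stop if P(θ_RES < 0.2 | data) > 0.97; looks at 6, 12, ..., 66 patients, 3 + 3 per look; control ORR about 20-40%.

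**Step 1: reproduce the printed ORR boundary.** With x responders among n patients in both arms, the posterior is Beta(0.8 + x, 1.2 + n − x). The boundary is the largest x for which P(θ < 0.2) > 0.97.

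- n = 12, x = 0: 0.965, so no stop is possible.
- n = 18: x = 0 gives 0.991 and x = 1 gives 0.937, so stop at 0.
- n = 66: x = 7 gives 0.975 and x = 8 gives 0.947, so stop at 7 or fewer.

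All printed ORR entries match with n equal to all patients. The boundary arithmetic is correct.

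**Step 2: stop probabilities.** Each look adds Bin(3, p_control) + Bin(3, p_CD24Fc) responders. Carry the distribution of the running total forward, remove the mass at or below the boundary at each look, and sum what is removed. The first possible stop (18 patients, no responders) can be checked by hand: 0.9^18 = 15.0% at 10% in both arms; 0.8^18 = 1.8% at 20% in both arms; 0.6^9 = 1.0% at control 40%, CD24Fc 0%.

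Totals over all looks to 66 evaluable, every outcome known at each look:

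| ORR, same in both arms | 10% | 20% | 30% | 40% |
|---|---|---|---|---|
| Stops | 74.1% | 8.9% | 0.45% | 0.02% |

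| Control ORR | 20% | 30% | 40% |
|---|---|---|---|
| CD24Fc ORR 0% | 73.6% | 27.4% | 5.4% |
| CD24Fc ORR 10% | 31.2% | 7.9% | 1.4% |

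Control 40% with CD24Fc 0% and 20% in both arms have the same pooled rate of 20%. The first is total loss of response and stops 5.4% of the time; the second is no drug effect and stops 8.9%.

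**Step 3: effect of the denominator.** Suppose unretreated patients count as non-responders and half are retreated (an assumption; the documents give no figure). True ORRs of 20, 30 and 40% then enter the table as 0.5 × 20 = 10%, 15% and 20%, and with no drug effect the rule stops 74%, 32% and 9% of the time. With 60% retreated the figures are 56%, 15% and 3%.

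**Step 4: the same rule on CD24Fc patients only.** Same prior and cut-off, looks every 3 evaluable CD24Fc patients. Boundary: 0 responses at 15, 18, 21; ≤1 at 24, 27; ≤2 at 30, 33.

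| True CD24Fc ORR | 0% | 5% | 10% | 20% | 30% |
|---|---|---|---|---|---|
| 33 evaluable | 100% | 83.7% | 46.4% | 7.1% | 0.7% |
| 18 evaluable | 100% | 46.3% | 20.6% | 3.5% | 0.5% |

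Like for like at 18 evaluable per arm (about half of 36 retreated, assumed) and CD24Fc ORR 10%, the pooled rule stops 17.6%, 5.3% and 1.2% of the time at control 20, 30 and 40%, against 20.6% for the CD24Fc-only rule.

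**Step 5: toxicity, for completeness.** With prior Beta(0.3, 1.7) and limit 0.333, all ten printed AE bounds match n = half the enrolled. Events from both arms count against that one-arm n, so whenever CD24Fc events alone would reach the bound, the total does too.

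**The case against.** The best defence is that the inference in 10.4 is conditional. If control ORR is at least 20% and allocation is 1:1, a true pooled rate below 20% does require a CD24Fc rate below 20%. That is right, and it is why the point is stated as dependence on a benchmark. What remains is that the benchmark is external, while a concurrent placebo arm that could test it is left unused at the interim.

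A reader might infer from the 74.1% that the rule often stops falsely under the plan's own assumptions. It does not: inside the 20-40% range, with every patient evaluable, no-effect stops are at most 8.9%. The 74.1% applies if the benchmark is too high for this population, or if unretreated patients are counted as non-responders.

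A reader might also infer that a low pooled rate would be reported as tumour promotion by CD24Fc. The sentence justifies a threshold and sets no reporting rule, and 10.2 plans a between-group comparison of response. That comparison covers the analysis but not the interim decision.

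Finally, a CD24Fc-only rule is no proof of a drug effect either: with 10% in both arms and 33 evaluable CD24Fc patients it stops 46.4% of the time. This stands, so such a stop has to be read beside the placebo ORR.

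**Conclusion.** The point holds for the ORR rule. The attribution to CD24Fc does not follow from a pooled rate without the external benchmark. Inside the plan's control range the main weakness is missed harm: total loss of response on CD24Fc goes undetected about 73% of the time at control 30% (100 − 27.4) and about 95% at control 40% (100 − 5.4). Below that range the weakness is stopping with no drug effect.

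A reader might say that the ORR denominator is missing. It is inconsistent rather than absent: 8.0.2.0 and 10.2 address it, but they do not agree with the post-retreatment definition in 10.4 or with a table indexed by all enrolled patients.

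A reader might extend the criticism to the pooled AE count. The documents do not support that: the pooling is disclosed as conservative and the 33.3% ceiling is protected. Only its false-stop rate is unstated.

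The figures assume exact 3 + 3 balance, independent patients, each rule acting alone, and all outcomes known at each look. The last is optimistic, because ORR follows a discretionary retreatment decision and a later tumour assessment. They are therefore boundary-crossing probabilities and do not show how early a stop would come. This should be fixed; the boundary arithmetic itself is sound.

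**What to change.** In Section 10.4:

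1. Delete the inference from a low pooled ORR to a CD24Fc effect.
2. Reconcile 8.0.2.0, 10.2 and 10.4 and use one ORR denominator, for example patients retreated with ICI and assessed.
3. Have the study statistician give ORR by arm to the existing DSMC, with investigators kept blinded.
4. Apply the existing prior and 0.97 cut-off to evaluable CD24Fc patients, with the boundary and stop probabilities of Step 4 printed in the plan.
5. State that the DSMC reads any such stop beside the placebo ORR. This comparison is also needed for a fall from 40% to 20%, which the CD24Fc-only rule catches only 7.1% of the time with 33 evaluable.
6. Leave the pooled toxicity boundary as a stop. Optionally state its stop rates with equal event rates in both arms: 0.6%, 5.7%, 25.6% and 59.3% at 10, 15, 20 and 25% (the placebo rate is not given, hence a range).

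The cost is wording, one recalculated table and by-arm counts for a committee that already meets monthly. There are two downsides. The CD24Fc-only rule cannot act before 15 evaluable CD24Fc patients, and it gains little if control ORR is 20% (20.6% against 17.6% with 18 per arm and CD24Fc at 10%). The gain is at control 30-40%.

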10.5 Emergency Unblinding

In situations where the Investigator believes that knowledge of the subject's treatment assignment is required to select appropriate continuing therapy for the disease under study, the Investigator may unblind

the patient's treatment assignment. The Investigator should make every effort to contact the medical monitor before unblinding a patient's treatment assignment unless the urgency of the case requires immediate action. All other members of the study team should remain blinded to treatment assignment.

11. SAFETY AND REPORTING REQUIREMENTS

11.0 Adverse Events

An adverse event (AE) is defined as any new untoward medical occurrence or worsening of a preexisting medical condition in a clinical investigation participant administered study drug and that does not necessarily have a causal relationship with this treatment. An AE can therefore be any unfavorable and unintended sign (such as an abnormal laboratory finding), symptom, or disease temporally associated with the use of investigational product, whether or not considered related to the investigational product.

11.0.0 Severity of Adverse Events

The severity of an AE is graded based on the NCI CTCAE version 5.0. The guideline is as follows:

Grade 1 (Mild):	Asymptomatic or mild symptoms. Requires clinical or diagnostic observations only. Intervention not indicated.
Grade 2 (Moderate):	Moderate symptoms. Minimal, local or non-invasive intervention indicated. Limits age-appropriate activities of daily living.
Grade 3 (Severe):	Severe or medically significant symptoms, but not life-threatening. Limits self-care activities of daily living. Requires hospitalization or prolongation of hospitalization.
Grade 4 (Life-threatening):	Life-threatening consequences. Requires urgent intervention.
Grade 5 (Fatal):	The event caused death.

11.0.1 Causality (Attribution) of Adverse Events

The investigator is to assess the causal relation of all AEs (i.e., whether there is a reasonable possibility that the study drug caused the event) using the following definitions:

Not Related: Another cause of the AE is more plausible; a temporal sequence cannot be established with the onset of the AE and administration of the investigational product; or, a causal relationship is considered biologically implausible.

Unlikely: The current knowledge or information about the AE indicates that a relationship to the investigational product is unlikely.

Possibly Related: There is a clinically plausible time sequence between onset of the AE and administration of the investigational product, but the AE could also be attributed to concurrent or underlying disease, or the use of other drugs or procedures. Possibly related should be used when the investigational product is one of several biologically plausible AE causes.

Probably Related: The AE is likely related to investigational product.

Related: The AE is clearly related to use of the investigational product.

Any other AE not listed as an expected event in the Investigator's Brochure or in this protocol will be considered unexpected.

11.0.2 Serious Adverse Events

Serious adverse event (SAE) means any untoward medical occurrence that at any dose:

- Results in **death**.
- Is **life-threatening** (Note: the term "life-threatening" refers to an event/reaction in which the patient was at risk of death at the time of the event/reaction. It does not refer to an event/reaction which hypothetically might have caused death if it were more severe).
- Requires inpatient **hospitalization or prolongation of an existing hospitalization**
- Results in **persistent or significant disability or incapacity**. (Disability is defined as a substantial disruption of a person's ability to conduct normal life functions).
- Is a **congenital anomaly/birth defect**.
- Is a **medically important event or reaction**. Medical and scientific judgment should be exercised in deciding whether other situations should be considered serious, such as important medical events that might not be immediately life-threatening or result in death or hospitalization, but might jeopardize the patient or might require intervention to prevent one of the other outcomes listed in the definition above.

11.1 Procedures for Reporting Adverse Events

11.1.0 Methods and Timing for Assessing and Recording Safety Variables

The investigator is responsible for ensuring that all AEs and SAEs that are observed or reported during the study are collected and reported to the IRB and to the FDA in accordance with CFR 312.32 (IND Safety Reports).

11.1.1 Adverse Event Reporting Period

The study period during which all AEs and SAEs must be reported begins at initiation of study treatment and ends 30 days following the last administration of study treatment or study discontinuation/termination, whichever is earlier. After this period, investigators should only report SAEs that are attributed to prior study treatment.

Investigators are not obligated to actively seek information regarding the occurrence of new SAEs beginning after the 30-day post last dose period. However, if the investigator learns of such an SAE and that event is deemed relevant to the use of study treatment, he/she should promptly document and report the event. A longer reporting period applies in the case of pregnancy.

11.1.2 Procedures for SAE Reporting

11.1.2.0 Reporting to the FDA

Sponsor of studies conducted under an IND are required to report all serious, unexpected, and related adverse events directly to the FDA on a MedWatch Form FDA 3500A within 7 (if fatal or life-threatening) or 15 calendar days of first awareness, as described below.

Before submitting this report, the sponsor needs to ensure that the event meets all three of the definitions contained in the requirement:

- Suspected adverse reaction
- Serious
- Unexpected

The Sponsor will notify the FDA according to the following timelines:

within **7 calendar days** of any unexpected fatal or life-threatening adverse event with possible relationship to study drug;

within **15 calendar days** of any event that is considered: 1) serious, 2) unexpected, and 3) at least possibly related to study participation.

FDA fax number for IND Safety Reports: **[name]** or **[contact]**

If the adverse event does not meet all three of the definitions, it should not be submitted as an expedited IND safety report to the FDA. For adverse events that are either serious but don't meet the criteria for expedited reporting or are not serious, the FDA will be notified at the time of the IND Annual Report.

MedWatch Form FDA 3500A Reporting Guidelines

In addition to completing appropriate demographic and suspect medication information, the report should include the following information within the Event Description of the MedWatch Form FDA 3500A:

- Treatment regimen (dosing, frequency, combination therapy)
- Protocol description (include number if assigned)
- Description of event, severity, treatment, and outcome, if known
- Supportive diagnostic and laboratory results
- Investigator's assessment of the relationship of the SAE to each investigational product and suspect medication
- Follow-up information:
- Additional information may be added to a previously submitted report by any of the following methods:
 - Adding to the original MedWatch Form FDA 3500A and submitting it as follow-up
 - Adding supplementary summary information and submitting it as follow-up with the original MedWatch Form FDA 3500A

- Summarizing new information and faxing it with a cover letter including subject identifiers (i.e., DOB, initials, subject number), protocol description and number, suspect drug, brief adverse event description, and notation that additional or follow-up information is being submitted

11.1.2.1 Reporting to the Institutional Review Board

Both serious and non-serious adverse events will be reported in accordance with UCD IRB Administration and UCD Comprehensive Cancer Center's (UCDCCC) Office of Clinical Research (OCR) policies. The UC Davis IRB can be reached at [contact].

Participating site(s) will report adverse events per institution's IRB guidelines.

12. ETHICAL CONSIDERATIONS AND ADMINISTRATIVE PROCEDURES

12.0 Ethics and Good Clinical Practice

This study must be carried out in compliance with the protocol and Good Clinical Practice, as described in:

1. International Council for Harmonisation (ICH) Harmonized Tripartite Guidelines for Good Clinical Practice 1996.
2. Directive 91/507/EEC, The Rules Governing Medicinal Products in the European Community.
3. US 21 Code of Federal Regulations dealing with clinical studies (including parts 50 and 56 concerning informed consent and IRB regulations).
4. Declaration of Helsinki, concerning medical research in humans (Recommendations Guiding Physicians in Biomedical Research Involving Human Subjects, Helsinki 1964, amended Tokyo 1975, Venice 1983, Hong Kong 1989, Somerset West 1996).

The investigator agrees, when signing the protocol, to adhere to the instructions and procedures described in it and thereby to adhere to the principles of Good Clinical Practice that it conforms to.

